8 STATISTICAL METHODOLOGY AND STATISTICAL ANALYSES

8.1 STATISTICAL METHODS

a. Sample Size Calculation:

The sample size can be estimated according to a desired sensitivity or specificity, and the choice of the N obtained will be defined by privileging to maximize the sensitivity (cut-off value defined > 0.8). The sample size necessary to demonstrate hypothesis will be defined. This calculation will be made at each of the interim analysis, to evaluate the total number of patients to be recruited. The sample size calculation formulas are defined

Formula of the sample size calculation dependent on Sensitivity

$$N(sN) = \frac{TP+FN}{P}$$

Where,

$$TP+FN = z^2 \times \frac{(SN(1-SN))}{W^2}$$

TP : Prevalence of ALK rearrangements in the population and / or in the data set of the interim analysis.

SN : Minimal acceptable sensitivity

W : Desired confidence interval, also called α (here a 99 % is desired)

z : Constant dependent on the desired confidence interval, this value is obtained from the table of the normal distribution. For a 95 % confidence interval the value of z is 1.96, and for a range of 99 %, it is 2.58.

i. Formula of the calculation of the sample size dependent on the Specificity:

$$N(sP) = \frac{FP+TN}{(1-P)}$$

Where,

$$FP+TN = z^2 \times \frac{(SP(1-SP))}{W^2}$$

P : Prevalence of ALK rearrangements in the population and / or in the data set of the interim analysis.

SP : Minimal acceptable specificity

W : Desired confidence interval, also called α (here a 99 % is desired)

z : Constant dependent on the desired confidence interval, this value is obtained from the table of the normal distribution. For a 95 % confidence interval the value of z is 1.96, and for a range of 99 %, it is 2.58

b. Concordance test:

i. Test type:

The agreement between Ventana ALK and NGS assay for ALK will be evaluated based on the Binary Qualitative type (Two tails), where the results can only have two values (concordance, discordance). The following metrics will be evaluated from the results:

- *Sensitivity:* $\frac{TP}{(TP+FN)}$
- *Specificity:* $\frac{TN}{(TN+FP)}$

- *Precision: PPV* = $\frac{TP}{(TP+FP)}$
- *Accuracy*: $\frac{TP+TN}{TP+TN+FP+FN}$
- Limit of detection (LOD): They will be established a priori by the reference values delivered by Thermo Fisher. After the interim analysis, these will be re-evaluated and / or modified. Among the influential values in the limits of detection are: the coverage

ii. Concordance methods:

Each of the following methods could be affected differently by the proportion of positive and negative cases; therefore both methods will be used.

Simple Agreement: Simple agreement will be calculated as the concordance proportion for the positive cases (PPA), and the concordance proportion for the negative cases (NPA).

Specific Agreement:

To establish the specific agreement we will use two methods **McNemar’s Chi-Square** and **Cohen’s Kappa**. The objective is to establish the statistical significance (P-value) of the correlation between the results obtained for ALK using NGS y Ventana®. However, previous investigation establish that these methods tend to reject the hypothesis H0.

- **McNemar’s Chi-Square:** This method is easier to calculate and more precise when the discordance is small compared with the concordance agreement.

For the following variables:

	Test 2 Positive	Test 2 Negative	Totals
Test 1 Positive	a	b	n ₁ =a+b
Test 1 Negative	c	d	n ₂ =c+d
Totals	m ₁ =a+c	m ₂ =b+d	N=n ₁ +n ₂

Where, the null hypothesis is H₀: p_b=p_c and the alternative hypothesis is H₁: p_b≠p_c.

The McNemar’s test statistic with Yates' continuity correction is:

$$X^2 = \frac{(|b-c|-1)^2}{b+c} \quad , \text{ with degree of freedom } = 1$$

Under the null hypothesis, with a sufficiently large number of discordant (cells b and c), X^2 has a chi-squared distribution with 1 degree of freedom. If the X^2 result is significant, this provides sufficient evidence to reject the null hypothesis, in favour of the alternative hypothesis that $p_b \neq p_c$, which would mean that the marginal proportions are significantly different from each other. If either b or c is small ($b + c < 25$) then X^2 is not well-approximated by the chi-squared distribution and a modification at this method will be required.

Cohen’s Kappa: Kappa measures the percentage of data values in the main diagonal of the table and then adjusts these values for the amount of agreement that could be expected due to chance alone.

For the following variables:

The cell

	Test 2 Positive	Test 2 Negative	Totals
Test 1 Positive	a	b	$n_1=a+b$
Test 1 Negative	c	d	$n_2=c+d$
Totals	$m_1=a+c$	$m_2=b+d$	$N=n_1+n_2$

table below contains

probabilities (P) of each type of results in 2 by 2 table.

To

	Test 2 Positive	Test 2 Negative	Totals
Test 1 Positive	P_a	P_b	
Test 1 Negative	P_c	P_d	
	$P_{(a+c)}$	$P_{(b+d)}$	1

calculate Kappa, first is

necessary to calculate the observed level of agreement $P_0 = P_a + P_d$

P_0 is then compared to the value obtained if both methods were totally independent $P_e = (P_{(a+c)})^2 + (P_{(b+d)})^2$

$$K = \frac{(P_o - P_e)}{(1 - P_e)}$$

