7.4 Study size

The results regarding the presence or absence of specific gene fusions (ALK and/or ROS1) after applying NGS will be confirmed using certified and validated test for clinical use, which will allow the specificity of NGS test for the analyzed gene. In all participant subjects the presence of gene ALK and ROS1 variation will be analyzed which will allow to estimate the sensitivity in the NGS test.

The specificity of the NGS trial will be calculated based on cases with a particular gene fusion where a result has been obtained through a certified test. Thus, the specificity will be equal to the confirmed cases through certified test divided by the total of NGS identified mutated cases number. The sensitivity will be calculated dividing the number of cases with a confirmed gene fusion by an ALK and/or ROS1 certified test by the number of the same cases in which the fusion was identified by NGS.

The gene fusion in ROS1 has been selected as the primary variation for the statistical analysis plan, since is the less frequent variation in lung cancer (COSMIC Sanger Database) with a prevalence of 1-2%. The confidence intervals for sensitivity and specificity will be calculated according to the efficiency method of the marker (efficient score method, Newcombe, 1998, Wilson, 1927).^{19, 20}

This study expects to analyze a total of 30 tumors with alterations in the ROS1 gene and 120 alterations in ALK. Thus, for a precision up to 80% (either specificity or sensitivity), will be enough information to establish a sensitivity and specificity estimation of the NGS trial within 0.1 points and 0.05 points (wide of 95% of the confidence interval) respectively.

Given an estimated prevalence of ROS1 at 1-2% and ALK at 3-5% for NSCLC, an initial set of 1000 patients will be screened.

An interim analysis will be performed at the first 1000 NSCLC samples to evaluate prevalence rates. If anticipated prevalence rates do not align with determined prevalence rates at this stage, an additional 2000 patients will be screened for a potential total of 3000 patients.

A subsequent interim analysis will be performed at the 3000 NSCLC samples to evaluate prevalence rates. If anticipated prevalence rates do not align with

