The Ion PGM Sequencer uses the reagents provided in the Ion PGM Sequencing Kit to detect nucleotide incorporation on the chip. The signal generated by the sequencing reaction on the 318 chip is translated into base calls and then reads. The DNA reads are 'mapped' to the reference human genome (hg19) followed by detection of SNVs, Indels, and CNVs.

The RNA reads are 'mapped' to a reference containing control sequences and candidate gene fusion sequences. Gene fusions are detected as present if they map to these sequences and pass certain filtering criteria.

The end result of this workflow is a set of variant calls that correspond to the original sample. The Ion PGM Torrent Suite software will call out any variation between the Reproducibility Sample member sequence at the locations designated in the Hot Spot file. This process is executed using the Ion PGM Torrent Suite software which runs on the Ion Torrent Server. The Ion PGM Torrent Suite software manages the complete end-to-end workflow from sample to variant call.

The clinical data will be recorded in an electronic case report form (eCRF) managed digitally in the platform Medsharing. This system allows tracking and controlling the clinical

information associated to the specimen. It is based in an online interface that allows the centralized management of multiple clinical sites.

Study population

The study population includes all patients who satisfy all inclusion and do not present any of the exclusion criteria detailed in the protocol.

Inclusion Criteria (according with amendment 2, 23 November 2017)

- 1. Men or women 18 years of age or older.*
- 2. Patients with a diagnosis of non-small cell carcinoma (NSCLC) histologically or cytologically tested.*
- 3. When a blood sample is donated, the individual must have an active tumor, i.e. the patient has a tumor in the moment of blood collection. The diagnosed is based on image test i.e.: X- RAY, Ct SCAN, RMN, PET Scan and among other, and biopsy (liquid or standard).*
- 4. Informed consent form, signed and dated, stating that the patient (or the legal representative) has been informed of all relevant aspects of the clinical study before being incorporated into the study, when appropriate.*
- 5. Patients must give consent for the research use of their tissues on file or fresh or 2 tubes of blood if available, or both.*

Exclusion criteria

Patients who meet some of the following criteria will not be included in the study:

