7 HANDLING OF MISSING VALUES

- **Clinical Data:**
 - Retrospective patients without information whether or not Smoker -> Patient is eliminated from the secondary analysis (of the smokers' subgroup).
 - Patients without PI data (the PI did not provide the information) -> Patient is removed from the secondary analysis (of the subset)
 - Patient without ALK data -> Patient is eliminated from primary analysis.
- **Sequencing:**
 - Insufficient sample: If at least 20 ug of DNA and 20 ug RNA or both are not obtained, the sample is eliminated from the primary analysis. The data will be used to establish pre-analytical QC parametric.
 - Samples within the sequencing flow: if BAM files have not been generated, the sample is eliminated from the primary analysis. For the final analysis just samples with BAM files will use to perform the genomic analysis, those samples without BAM files but that are not within the sequencing flow will be considered for the QC analytics.
- **Bioinformatics:**
 - Sample without cellularity, 100% cellularity will be assumed; the missing data will be recorded, the sample is included in all analyzes, except those where this variable is considered for QC analytics.
 - Sample without gender, UNK gender will be assumed (The team in case of UNK assumes as MALE), the missing data will be recorded, the sample is included in all analyzes. Except those where the subgroup is used for analysis.
 - DNA sample fails in QC parameters, it is eliminated from DNA dependent analysis, but it is included in primary analysis
 - RNA sample fails in QC parameters, primary analysis is eliminated.
- **** There are special cases where the primary analysis could be answered with defective samples, should it continue? Remove from the primary analysis, but group in special cases to analyze later.**

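### SAP 8.1a uses a number of evaluable patients as the recruitment total, with no allowance for the SAP 7 removals or for blood-only patients

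*SAP*

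**What the plan says.** SAP 8.1a sizes the study from a target sensitivity or specificity, "privileging to maximize the sensitivity (cut-off value defined > 0.8"). The sensitivity version is N = (TP+FN)/P with TP+FN = z²·SN(1−SN)/W². The specificity version is N = (FP+TN)/(1−P). P may come from the population, from the interim data set, or from both. The purpose is explicit: "This calculation will be made at each of the interim analysis, to evaluate the total number of patients to be recruited". SAP 3 agrees: the first interim defines the sample size, and the second fixes the total recruitment needed for power.

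SAP 7 then takes four groups out of the primary analysis: patients with no ALK result, samples with too little nucleic acid, samples with no BAM file, and samples failing RNA quality control ("RNA sample fails in QC parameters, primary analysis is eliminated"). SAP 2.1, inclusion criterion 5, accepts consent for "tissues on file or fresh or 2 tubes of blood if available, or both". The same section runs both the ALK reference test and NGS on FFPE tissue. Protocol 7.1.1, by contrast, requires consent to tissue use and treats blood as optional.

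The protocol's targets are counts of analysed samples. Section 7.4 says "This study expects to analyze a total of 30 tumors with alterations in the ROS1 gene", with 120 for ALK. The Abstract derives a need to screen at least 3000. It adds 3000 more, to a potential 6000, if prevalence does not align or the 30 and 120 are not obtained. Protocol 7.4 repeats the extension steps on prevalence alone. SAP 3 ties the step from 1000 to 3000 to prevalence alone.

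**The concern.** TP+FN is the number of reference-positive patients whom NGS has also classified. Dividing it by prevalence gives the number of patients who must have both results. That equals the number to recruit only if every recruit has both. The SAP itself says this will not be so, and Protocol 7.2 names the likely causes: too few slides for RNA extraction, poor FFPE handling, and RNA that is scant or of bad quality. Neither the formula nor the 3000 contains a term for these losses.

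If recruitment stopped at the computed N, fewer positives would be analysed than planned and the sensitivity interval would be wider than intended. The prevalence-only extension rule may not catch this. If failures are unrelated to ALK status, prevalence among evaluable samples stays the same however many samples are lost. This point concerns sizing only, not whether excluding failed samples biases sensitivity.

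**Working it through.** **1. The protocol's own figure.** The Protocol Abstract expects 10 ROS1+ and 40 ALK+ per 1000, that is 1% and 4%. Required positives divided by prevalence gives 30/0.01 = 3000 and 120/0.04 = 3000. Both match the stated 3000, and both assume no loss.

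**2. Effect of loss on 3000 screened.** The documents give no E, so 0.9, 0.8 and 0.7 are assumed. Analysed positives = 3000 × prevalence × E. The half-width is the 95% Wilson half-width at a proportion of 0.80, h = z·√(p(1−p)/n + z²/(4n²)) / (1 + z²/n), with z = 1.96. For n = 120 this is 0.0733/1.0320 = 0.071.

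| E | ALK+ analysed | half-width | ROS1+ analysed | half-width | recruits to keep 120 and 30 (3000/E) |
|---|---|---|---|---|---|
| 1.0 | 120 | 0.071 | 30 | 0.139 | 3000 |
| 0.9 | 108 | 0.075 | 27 | 0.146 | 3334 |
| 0.8 | 96 | 0.079 | 24 | 0.154 | 3750 |
| 0.7 | 84 | 0.085 | 21 | 0.164 | 4286 |

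**3. The SAP formula.** It returns no number as written, because W is described as a confidence level: "W : Desired confidence interval, also called α (here a 99 % is desired"). To see how it behaves, take SN = 0.8, z = 2.58 (the SAP's 99% value), P = 0.04 and an assumed half-width W = 0.10. Then TP+FN = 2.58² × 0.16/0.01 = 106.5, and N = 106.5/0.04 = 2663. With 1/E applied, N becomes 2959 (E = 0.9), 3329 (0.8) or 3804 (0.7). If 2663 were recruited anyway, the normal-approximation half-width 2.58·√(0.16/(106.5·E)) would be 0.105, 0.112 or 0.120 instead of 0.10.

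**4. Which P is used.** Suppose 1000 recruits, 800 evaluable, and 32 positives among the evaluable.
- P among evaluable = 32/800 = 0.04, so N = 2663. This omits the loss. A population prevalence of 4% does the same.
- P over all recruits = 32/1000 = 0.032, so N = 106.5/0.032 = 3329. This already contains the loss, and dividing again by E = 0.8 would count it twice.

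The SAP does not say which denominator applies. The second choice also does not repair the specificity formula. There 1−P would be 0.968, whereas evaluable negatives are 768/1000 = 0.768 of recruits.

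**5. Room in the planned maximum.** At 6000 and 1%/4%, the targets survive a loss of up to 1 − 3000/6000 = 50%. If ALK is 3%, 120/0.03 = 4000 evaluable patients are needed, and the tolerable loss is 1 − 4000/6000 = 33%.

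**The case against.** A reader might infer that the 120 and 30 targets will be missed. The documents do not support that. The targets are protocol counts, worded as samples to analyse, and not outputs of this ALK-only formula. The Abstract extends screening to 6000 if they are not obtained, which absorbs a loss of roughly 33% to 50%. Even 3000 can suffice at higher prevalence. At 5% ALK, 120/0.05 = 2400 are needed, so a 20% loss is tolerable. At 2% ROS1, 30/0.02 = 1500 are needed, so a 50% loss is tolerable. What remains open is that the Abstract does not say whether a positive is counted at screening or after the SAP 7 removals, and that Protocol 7.4 and SAP 3 do not carry the count trigger.

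Three further points count against the concern. First, P taken as evaluable positives over all recruits would already include the loss in the sensitivity formula; this is possible but nowhere stated. Second, the sample-size re-assessments (SAP Appendices 4, 5, 7 and 8) are listed by title only in the text available, so an allowance there cannot be excluded. The governing formula should still state it. Third, no failure rate or blood-only rate is given, so the actual size is unknown.

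The gap between the 0.1 and 0.05 in Protocol 7.4 and the zero-loss half-widths of 0.139 and 0.071 should not be put down to attrition. If those figures are half-widths, the gap exists without any loss and is a separate matter.

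**Conclusion.** The concern holds as an omitted allowance in the sizing rule. The protocol's division itself is correct. As written, SAP 8.1a gives a recruitment total that is too small by 1/E whenever P is a population prevalence or a prevalence among evaluable samples. At an assumed E of 0.7 to 0.9 the total should be about 11% to 43% larger (1/0.9 to 1/0.7). For 3000 screened at 1% and 4%, this means 84 to 108 analysed ALK positives and 21 to 27 ROS1 positives. The loss of precision is modest: up to 0.014 in half-width for ALK (0.071 to 0.085) and up to 0.025 for ROS1 (0.139 to 0.164). These figures rest on the assumed E, and on failures and blood-only entry being unrelated to fusion status. A shortfall against 120 and 30 is a risk. It arises mainly if positives are counted before the removals or if only the prevalence trigger is applied.

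**What to change.** In SAP 8.1a:
- Define P as the prevalence among tissue patients with a valid reference result and a valid NGS result.
- Set N_recruit = (TP+FN)/(P × E) and (FP+TN)/((1−P) × E), with E the proportion of tissue-providing recruits who remain after the SAP 7 removals at that interim.
- Leave blood-only patients out of N, P and E alike, so that all three share one denominator, and reconcile SAP inclusion criterion 5 with Protocol 7.1.1.

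In the Protocol Abstract, Protocol 7.4 and SAP 3:
- Count the 120 ALK (reference-positive) and 30 ROS1 targets after the SAP 7 removals. For ROS1, use positivity by the confirmatory test where it was done, because Protocol section 5 says only that a parallel ROS1 test may be needed.
- Use that count as the extension trigger in all three places.

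If recruitment is not extended within the 6000, restate the precision at the evaluable count. This is the practical option if collection ended in June 2019 as planned.

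The cost is a few lines of text. For the 120 and 30 targets, the recruitment number rises but stays within 6000 for losses up to the 33% to 50% shown above. Otherwise, the stated precision becomes slightly less favourable.

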determined prevalence rates at this stage, an additional 3000 patients will be screened for a potential total of 6000 patients. The overall screening will occur at 3 or more sites. Patients will only participate in the study for the initial sample collection period.

The study will be completed in approximately 48 months. Since it's a non-interventional multi-center study involving the collection and analysis of FFPE tumor tissue and blood of NSCLC patients, patients will not be treated as part of the protocol.

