3 INTERIM ANALYSES

Given an estimated prevalence of ROS1 at 1-2% and ALK at 3-5% for NSCLC, an initial set of 1000 patients will be screened. An interim analysis will be performed at the first 1000 NSCLC samples to evaluate prevalence rates.

The first interim analysis will be carried out for the purpose of monitoring the overall progress of the study and to define the sample size of the study.

We expect that after the interim analysis changes in the final total number of recruited patient occur.

If anticipated prevalence rates do not align with determined prevalence rates at this stage, an additional 2000 patients will be screened for a potential total of 3000 patients.

A subsequent interim analysis will be performed at the 3000 NSCLC samples to evaluate prevalence rates. The main objective of this interim analysis is to determine the number of total recruited patients needed to get the statistical power.

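### SAP 8.1a defines W, the precision term in both sample-size formulas, as the confidence level and gives no half-width; separately, the protocol abstract, protocol 7.1 and 7.4, and SAP 3 state different rules for expanding the sample.

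*SAP*

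**What the plan says.** **Formula.** SAP 8.1a gives the number of positives as z² × SN(1 − SN)/W², divided by prevalence to obtain N, and a matching formula for specificity. Under both, the legend reads "W : Desired confidence interval, also called α (here a 99 % is desired". The next legend entry takes z from the confidence level: 1.96 for 95%, 2.58 for 99%. The choice of N is made by "privileging to maximize the sensitivity (cut-off value defined > 0.8". No figure is given for specificity. On use, the SAP says: "This calculation will be made at each of the interim analysis, to evaluate the total number of patients to be recruited".

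**Precision elsewhere.** Protocol 7.4 expects 30 ROS1 and 120 ALK tumours, takes a value of 80%, and says sensitivity and specificity will be estimated "within 0.1 points and 0.05 points (wide of 95% of the confidence interval) respectively".

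**Expansion.**
- The protocol abstract (Study Design) calls for at least 3000 samples. It then adds 3000 if prevalence does not align and/or if 30 ROS1+ and 120 ALK+ have not been obtained.
- Protocol 7.1 ties sampling of up to 6000 to obtaining at least 30 ROS1+.
- Protocol 7.4, at 1000: "If anticipated prevalence rates do not align with determined prevalence rates at this stage, an additional 2000 patients will be screened". At 3000 the condition is again non-alignment with the "determined prevalence rates at this stage, an additional 3000 patients will be screened for a potential total of 6000 patients". It has no count condition at either step.
- SAP 3 repeats the trigger at 1000, but says the first interim also serves for "monitoring the overall progress of the study and to define the sample size of the study". At 3000 it says only: "The main objective of this interim analysis is to determine the number of total recruited patients needed to get the statistical power".

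**The concern.** In a formula of this kind the confidence level belongs in z and the tolerated error in W. With W also defined as the confidence level, that level enters twice and the tolerated error not at all. A reader can guess that a half-width was meant, but not its size, and N varies with 1/W². The result is supposed to set total recruitment, so an unstated W leaves the study size undetermined.

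The expansion texts raise a second, separate question. The same interim counts could call for 3000 more patients under one text and for none under another, and nothing says which text governs or whether the counts or the formula decide.

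**Working it through.** **Inputs.** Sensitivity 0.8 (SAP 8.1a); ALK prevalence 3–5%, with 4% as centre (protocol 7.4; the abstract's tentative 40 ALK+ per 1000 is 4%); z = 1.96 or 2.58 (SAP 8.1a); precision figures 0.1 and 0.05 (protocol 7.4). Results are rounded to the nearest whole number.

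**1. The plan's own figures.** The yields reproduce: 1000 × 1% = 10 and 1000 × 4% = 40; 3000 × 1% = 30 and 3000 × 4% = 120. The precision does not. At 80%, the Wilson 95% interval (the method 7.4 names) is:
- 24/30: 0.627 to 0.905, half-width 0.139, full width 0.278
- 96/120: 0.720 to 0.862, half-width 0.071, full width 0.142

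Neither the half-widths nor the full widths equal 0.1 and 0.05, so the arithmetic in 7.4 does not show which was meant.

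**2. W as defined.** N = z² × 0.8 × 0.2 / W² / P, with z² × 0.16 = 6.6564 × 0.16 = 1.065 at z = 2.58.
- W = 0.99: 1.065/0.9801 = 1.09 positives; N = 1.09/0.04 ≈ 27 (22 to 36 for prevalence 5% to 3%)
- W = 0.01: 1.065/0.0001 = 10,650 positives; N = 266,256 (213,005 to 355,008)

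**3. W as a half-width.** Two points in 7.4 are open. *Respectively* may pair 0.1 and 0.05 with sensitivity and specificity, or with ROS1 (30) and ALK (120). *Wide* may mean half or full width. For ALK sensitivity:

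| Reading of 7.4 | W | Positives, 95% / 99% | N at 4%, 95% (5% to 3%) | N at 4%, 99% (5% to 3%) |
|---|---|---|---|---|
| Sens/spec, half-width | 0.10 | 61.5 / 106.5 | 1,537 (1,229–2,049) | 2,663 (2,130–3,550) |
| Sens/spec, full width; or ROS1/ALK, half-width | 0.05 | 245.9 / 426.0 | 6,147 (4,917–8,195) | 10,650 (8,520–14,200) |
| ROS1/ALK, full width | 0.025 | 983.4 / 1,704.0 | 24,586 (19,669–32,782) | 42,601 (34,081–56,801) |

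At the same W and an assumed specificity of 0.8, the specificity formula divides by 0.96 instead of 0.04. Its N is therefore 24 times smaller, and sensitivity governs.

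**4. What the ALK counts deliver.** Half-width = z × √(0.16/n).
- n = 120 (expected at 3000, 4%): 0.072 at 95%, 0.094 at 99%
- n = 240 (expected at 6000, 4%): 0.051 at 95%, 0.067 at 99%

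So 120 ALK+ meets 0.10 at either level and misses 0.05 at either level.

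**5. Expansion rules at 1000.** If prevalence aligns at 1%/4%, protocol 7.4 and the matching sentence in SAP 3 trigger nothing. The expected counts are then 10 and 40, one third of the targets. The abstract requires at least 3000 regardless.

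**6. Expansion rules at 3000.** The abstract (read as *or*) and 7.4 part company when prevalence aligns but a count target is missed. *Align* has no stated tolerance, so two assumptions were tried at true rates of 1% ROS1 and 4% ALK, treating the two as mutually exclusive (exact trinomial).
- Observed rates within 1–2% and 3–5% (30–60 ROS1+, 90–150 ALK+): P(aligned) = 0.522, P(both targets met) = 0.266, P(aligned but a target missed) = 0.258.
- Reaching the anticipated 1%/4% yield (at least 30 and at least 120): aligned and met are the same event, so the divergence is 0.

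**The case against.** The strongest reply on the formula is that W is a labelling slip. Any statistician would read it as a margin, and an N of 27 or 266,256 would be rejected on sight. That is fair as to the literal values, but it does not supply the missing number. Protocol 7.4 is the only place to look, and it leaves three candidates at 95%, where the SAP asks for 99% without a reason.

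A reader might infer that 7.4 plainly means 0.1 for sensitivity, so that 120 ALK+ is enough. The documents do not support that. 7.4 has just listed 30 ROS1 and 120 ALK, and √(120/30) = 2 matches 0.1/0.05, which favours the gene pairing; under it, 120 ALK+ falls short.

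On expansion, a reader might infer that the plan stops early, or that 7.4 and the abstract would often conflict at 3000. Neither is shown. No stopping rule is stated, the milestones (protocol 4) plan for 6000, protocol 7.1 links that figure to a ROS1 count, and the abstract's targets are exactly its tentative yield scaled to 3000. SAP 3 also does not revoke the protocol's 6000 cap by leaving it out.

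Finally, SAP appendices 4, 5, 7 and 8 are titled as sample-size re-assessments and may record the W used. The SAP also cites a protocol amendment 2 that the supplied protocol does not show, so some differences may come from versions. Both points stand. They limit what can be said about harm, but they do not correct the definition in 8.1a.

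**Conclusion.** The definition of W is wrong as written in both formulas, and the visible text does not supply the value it needs. At sensitivity 0.8 and ALK prevalence 4%, the readings that 7.4 allows run from N = 1,537 to 24,586 at 95%, a 16-fold range since (0.10/0.025)² = 16, and from 2,663 to 42,601 at 99%.

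The expansion texts do differ and need one rule. The size of that problem at 3000 is not fixed by the documents: at true rates of 1%/4% the chance of divergence is 0.26 under one assumed tolerance and zero under another. The difference at 1000 does not depend on such an assumption.

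It does not follow that the study recruited the wrong number. The W and the rule actually applied are not visible.

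**What to change.** **SAP 8.1a.** In both formulas, define W as the half-width of the confidence interval and remove the equation with α. State a value for sensitivity and one for specificity at a single confidence level: 95% to match protocol 7.4, or 99% with a reason. Label prevalence P in the sensitivity legend, which now calls it TP.

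**Protocol 7.4.** Say what *respectively* pairs and whether *wide* is a half or full width.

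**Expansion.** Reconcile the abstract, protocol 7.1, protocol 7.4 and SAP 3 to one rule, chosen by the sponsor. Replace *and/or* with one word, define *align* if it stays, and say whether the counts or the formula set the final N. If the formula asks for more than 6000, keep the cap and report the precision for the ALK+ number actually obtained, using the half-widths in step 4 as a guide.

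**Cost.** The W and 7.4 changes are wording and stated values. Choosing the expansion rule is a trade-off: at true 1%/4%, keeping the count condition adds 3000 × 0.258 = 774 expected patients over 7.4 alone under the first assumption in step 6, and none under the second, all within the 6000 cap. Data collection was planned to end in June 2019 and SAP 2.0 is dated July 2019. If recruitment has closed, the task is only to document the W and the rule applied at each interim.

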The endpoint of this Project will be to analyze 30 positive ROS1 and 120 positive ALK samples to validate the diagnostic method.

Given an estimated prevalence of ROS1 at 1-2% and ALK at 3-5% for NSCLC, an initial set of 1000 patients will be screened. An interim analysis will be performed at the first 1000 NSCLC samples to evaluate prevalence rates (tentatively 10 ROS1+ and 40 ALK+).

For the majority of molecular tests, it is expected that at least 50 positive patient samples be utilized for validation, and ideally at least 10 positives representing each variant being detected¹. Given the low prevalence of ROS1 which has 16 unique variants and recent analysis demonstrating that in 30 ROS1+ patient samples, there is representation of the 3 dominant variants suitable for analytical validation², it is necessary to screen at least 3000 NSCLC samples for identifying positive samples for both ROS1 and ALK that should be sufficient for analytical validation of the NGS platform. If anticipated prevalence rates at the 3000 sample mark do not align with determined prevalence rates at this stage and/or 30 positive ROS1 and 120 positive ALK samples are not obtained, an additional 3000 patients will be screened for a potential total of 6000 patients. The overall screening will occur at 3 or more sites. Patients will only participate in the study for the initial sample collection period.

The study will be completed in approximately 48 months.

Study Treatment

None.

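### The SAP's chance-agreement term for Cohen's kappa squares one test's margins, so kappa is wrong whenever the assays' positive rates differ and depends on which assay is called Test 2

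*SAP*

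**What the plan says.** SAP section 8.1 (b.ii, Concordance methods) names two specific-agreement methods for NGS against Ventana ALK: McNemar's test and Cohen's kappa. It states their purpose: "The objective is to establish the statistical significance (P-value) of the correlation between the results obtained for ALK using NGS y Ventana". Kappa is described as a measure that "adjusts these values for the amount of agreement that could be expected due to chance alone". Observed agreement is Po = Pa + Pd, and kappa is (Po − Pe)/(1 − Pe). The chance term is defined as follows:

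"P_0 is then compared to the value obtained if both methods were totally independent $P_e = (P_{(a+c)})^2 + (P_{(b+d)})^2"

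In the count table just above, rows are Test 1 (n1 = a+b, n2 = c+d) and columns are Test 2 (m1 = a+c, m2 = b+d). Section 8.1 does not say which assay is Test 1 and which is Test 2. No other kappa formula appears in either document, and SAP Appendix 2, meant for further statistical detail, is marked not applicable.

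**The concern.** The text describes agreement expected under independence, but the formula does not compute it. Two independent tests are both positive with probability P(a+b) × P(a+c) and both negative with probability P(c+d) × P(b+d). The SAP squares the two Test 2 column margins instead, which assumes that Test 1 has the same positive rate as Test 2. It does not pool the two tests' margins either, so it is not the pooled-margin alternative (Scott's pi).

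Equality of positive rates is what McNemar's test examines in the same section. One method therefore assumes what the other tests. Cohen's kappa does not change when the labels are swapped, but this version does, so one data set can give two values with nothing prespecified to choose between them. SAP section 4.1 says that the NGS–Ventana comparison is the only aim with a tested hypothesis.

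**Working it through.** The documents state no kappa value, so there is no plan figure to reproduce. The check applies the written formula and Cohen's formula to the same tables.

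**Inputs from the documents**
- ALK prevalence of 3–5% (SAP section 3).
- Expected yield at the first 1000 samples (protocol abstract, Study Design): "tentatively 10 ROS1+ and 40 ALK"-positive, which is 40/1000 = 4%.
- Target of 120 ALK positives, with at least 3000 samples to be screened (protocol abstract): 120/3000 = 4%.
- Sensitivity cut-off of 0.8 (SAP section 8.1 a).

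**Assumptions:** the error patterns of NGS against Ventana, and NGS as the row test.

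**Formulas.** Let p1 and p2 be the positive rates of Test 1 and Test 2.
- Cohen: Pe = p1 × p2 + (1 − p1)(1 − p2)
- SAP: Pe = p2² + (1 − p2)²
- Difference: SAP Pe − Cohen Pe = (p2 − p1)(2 × p2 − 1)

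At 3–5% prevalence with Ventana as Test 2, the factor 2 × p2 − 1 lies between −0.94 and −0.90. NGS under-calling (p1 < p2) therefore lowers Pe and inflates kappa, and over-calling deflates it. In these scenarios, swapping the labels reverses the direction. With p1 = p2 the difference is zero.

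**One case in full.** NGS misses 60 of 120 and has no false positives: a = 60, b = 0, c = 60, d = 2880.
- Po = 2940/3000 = 0.98; NGS rate 0.02; Ventana rate 0.04.
- Cohen: Pe = 0.02 × 0.04 + 0.98 × 0.96 = 0.9416; kappa = 0.0384/0.0584 = 0.658.
- SAP, Ventana as Test 2: Pe = 0.04² + 0.96² = 0.9232; kappa = 0.0568/0.0768 = 0.740.
- SAP, NGS as Test 2: Pe = 0.02² + 0.98² = 0.9608; kappa = 0.0192/0.0392 = 0.490.

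**All cases** (N = 3000, 120 Ventana-positive)

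| NGS against Ventana | a, b, c, d | Po | Cohen Pe | Cohen kappa | SAP kappa, Ventana = Test 2 | SAP kappa, NGS = Test 2 |
|---|---|---|---|---|---|---|
| Sensitivity 0.95, specificity 0.995 | 114, 14.4, 6, 2865.6 | 0.9932 | 0.9206 | 0.914 | 0.911 | 0.917 |
| Misses 24, adds none (sensitivity 0.8) | 96, 0, 24, 2880 | 0.992 | 0.9306 | 0.885 | 0.896 | 0.871 |
| Misses 24, adds 24 (equal margins) | 96, 24, 24, 2856 | 0.984 | 0.9232 | 0.792 | 0.792 | 0.792 |
| Misses none, adds 60 | 120, 60, 0, 2820 | 0.980 | 0.9048 | 0.790 | 0.740 | 0.823 |
| Misses 60, adds none | 60, 0, 60, 2880 | 0.980 | 0.9416 | 0.658 | 0.740 | 0.490 |
| Calls everything negative | 0, 0, 120, 2880 | 0.960 | 0.9600 | 0.000 | 0.479 | undefined |

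With Ventana as Test 2, the SAP's Pe is 0.9232 in every row, because it does not respond to NGS at all. In the last row this gives (0.96 − 0.9232)/0.0768 = 0.479 for an assay that detects nothing. At 3% and 5% prevalence the corresponding values are 0.48 and 0.47. With NGS as Test 2, Pe = 1 and the denominator is zero.

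**The case against.** The best defence is that the error may never matter. The SAP names Cohen's kappa, and a standard routine would compute it correctly whatever the printed formula says. When the assays agree well the distortion is small: about 0.003 at sensitivity 0.95 and specificity 0.995, and 0.011 to 0.014 at sensitivity 0.8 with no false positives. The 0.48 needs an assay that calls nothing positive and one particular labelling. The row with 60 missed is sensitivity 60/120 = 0.50, below the SAP's own cut-off.

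Such failures would also show elsewhere. Sensitivity and positive agreement would be zero in the all-negative case. The SAP's McNemar statistic would be (120 − 1)²/120 = 118 there and (60 − 1)²/60 = 58 in either 60-discordant case. SAP section 4.2 sets only p-value and FDR thresholds, and no kappa cut-off exists.

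All of this stands, and it limits the consequence. It does not rescue the formula. The SAP names no software, so a program written to the SAP would return the wrong value. The extreme case is a test of the chance correction, which the formula fails. The blank row-total cells in the SAP's probability table may be a PDF-reading artefact, and nothing here rests on them.

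**Conclusion.** The formula is wrong as written. It gives Cohen's kappa only when b = c; otherwise it is biased in a direction that depends on an unspecified labelling. At 4% prevalence the error runs from a few thousandths for closely agreeing assays to 0.03–0.17 when 60 of 3000 samples are discordant in one direction. It reaches 0.48 in the limiting case of an all-negative NGS with Ventana as Test 2. These sizes rest on assumed discordance patterns; the algebra does not. Sensitivity, specificity, PPV, accuracy, PPA, NPA and McNemar's test do not use Pe and are unaffected. This should be corrected because it concerns a named method for the only tested aim, but it does not by itself overturn the concordance analysis.

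**What to change.** In SAP section 8.1 (b.ii), replace the chance term with Pe = P(a+b) × P(a+c) + P(c+d) × P(b+d). State which assay is Test 1 and which is Test 2, and make sure that the probability table shows both tests' margins. With this change an all-negative assay gets kappa = 0, and sensitivity 0.8 with specificity 1.0 gives 0.885, under either labelling. Reporting kappa with a 95% confidence interval would be a sensible addition, though it is separate from this error.

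The cost is one formula line and a sentence on labels; no new data are needed. SAP version 2.0 is dated 10 July 2019, after the planned end of data collection on 30 June 2019. Any kappa already produced should therefore be checked, and recalculated if the printed formula was used.
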